### For Part B Outcome Measures

MDS-UPDRS Parts II and III are rated at baseline, EOT/ET, and the last follow up visits. MDS-UPDRS Parts II and III sub scores and total scores will be based on the observed and change from baseline data.

MDS-UPDRS part II questionnaire consists of the following items:

- UPDRS part 2 Speech (MDS\_201; Numeric: 0, 1, 2, 3, 4; Levels: Normal or Slight or Mild or Moderate or Severe)
- UPDRS part 2 Saliva and drooling (MDS\_202; Numeric: 0, 1, 2, 3, 4; Levels: Normal or Slight or Mild or Moderate or Severe)
- UPDRS part 2 Chewing and swallowing (MDS\_203; Numeric: 0, 1, 2, 3, 4; Levels: Normal or Slight or Mild or Moderate or Severe)
- UPDRS part 2 Eating tasks (MDS\_204; Numeric: 0, 1, 2, 3, 4; Levels: Normal or Slight or Mild or Moderate or Severe)
- UPDRS part 2 Dressing (MDS\_205; Numeric: 0, 1, 2, 3, 4; Levels: Normal or Slight or Mild or Moderate or Severe)
- UPDRS part 2 Hygiene (MDS\_206; Numeric: 0, 1, 2, 3, 4; Levels: Normal or Slight or Mild or Moderate or Severe)
- UPDRS part 2 Handwriting (MDS\_207; Numeric: 0, 1, 2, 3, 4; Levels: Normal or Slight or Mild or Moderate or Severe)
- UPDRS part 2 Doing hobbies and other activities (MDS\_208; Numeric: 0, 1, 2, 3, 4; Levels: Normal or Slight or Mild or Moderate or Severe)
- UPDRS part 2 Turning in bed (MDS\_209; Numeric: 0, 1, 2, 3, 4; Levels: Normal or Slight or Mild or Moderate or Severe)

- UPDRS part 2 Tremor (MDS\_210; Numeric: 0, 1, 2, 3, 4; Levels: Normal or Slight or Mild or Moderate or Severe)
- UPDRS part 2 Getting out of bed, a car or a deep chair (MDS\_211; Numeric: 0, 1, 2, 3, 4; Levels: Normal or Slight or Mild or Moderate or Severe)
- UPDRS part 2 Walking and balance (MDS\_212; Numeric: 0, 1, 2, 3, 4; Levels: Normal or Slight or Mild or Moderate or Severe)
- UPDRS part 2 Freezing (MDS\_213; Numeric: 0, 1, 2, 3, 4; Levels: Normal or Slight or Mild or Moderate or Severe)

MDS-UPDRS part III questionnaire consists of the following items:

- MDS-UPDRS 3a Medication use for patient's clinical state (MDS\_3a; Numeric: 0, 1; Levels: No or Yes)
- MDS-UPDRS 3b Patient's clinical state on medication (MDS\_3b; Numeric: 0, 1, 2; Levels: ON or OFF or N/A. No medication)
- MDS-UPDRS 3c On levodopa (MDS\_3c; Numeric: 0, 1; Levels: No or Yes)
- UPDRS part 3 Speech (MDS\_301; Numeric: 0, 1, 2, 3, 4; Levels: Normal or Slight or Mild or Moderate or Severe)
- UPDRS part 3 Facial Expression (MDS\_302; Numeric: 0, 1, 2, 3, 4; Levels: Normal or Slight or Mild or Moderate or Severe)
- UPDRS part 3 Rigidity LLE (MDS\_303\_LLE; Numeric: 0, 1, 2, 3, 4; Levels: Normal or Slight or Mild or Moderate or Severe)
- UPDRS part 3 Rigidity LUE (MDS\_303\_LUE; Numeric: 0, 1, 2, 3, 4; Levels: Normal or Slight or Mild or Moderate or Severe)
- UPDRS part 3 Rigidity Neck (MDS\_303\_Neck; Numeric: 0, 1, 2, 3, 4; Levels: Normal or Slight or Mild or Moderate or Severe)
- UPDRS part 3 Rigidity RLE (MDS\_303\_RLE; Numeric: 0, 1, 2, 3, 4; Levels: Normal or Slight or Mild or Moderate or Severe)
- UPDRS part 3 Rigidity RUE (MDS\_303\_RUE; Numeric: 0, 1, 2, 3, 4; Levels: Normal or Slight or Mild or Moderate or Severe)
- UPDRS part 3 Finger tapping – Left (MDS\_304\_L; Numeric: 0, 1, 2, 3, 4; Levels: Normal or Slight or Mild or Moderate or Severe)
- UPDRS part 3 Finger tapping – Right (MDS\_304\_R; Numeric: 0, 1, 2, 3, 4; Levels: Normal or Slight or Mild or Moderate or Severe)
- UPDRS part 3 Hand movements – Left (MDS\_305\_L; Numeric: 0, 1, 2, 3, 4; Levels: Normal or Slight or Mild or Moderate or Severe)
- UPDRS part 3 Hand movements – Right (MDS\_305\_R; Numeric: 0, 1, 2, 3, 4; Levels: Normal or Slight or Mild or Moderate or Severe)
- UPDRS part 3 Pronation-supination movement of hands – Left (MDS\_306\_L; Numeric: 0, 1, 2, 3, 4; Levels: Normal or Slight or Mild or Moderate or Severe)
- UPDRS part 3 Pronation-supination movement hands – Right (MDS\_306\_R; Numeric: 0, 1, 2, 3, 4; Levels: Normal or Slight or Mild or Moderate or Severe)
- UPDRS part 3 Toe tapping – Left (MDS\_307\_L; Numeric: 0, 1, 2, 3, 4; Levels: Normal or Slight or Mild or Moderate or Severe)
- UPDRS part 3 Toe tapping – Right (MDS\_307\_R; Numeric: 0, 1, 2, 3, 4; Levels: Normal or Slight or Mild or Moderate or Severe)
- UPDRS part 3 Leg agility – Left (MDS\_308\_L; Numeric: 0, 1, 2, 3, 4; Levels: Normal or Slight or Mild or Moderate or Severe)
- UPDRS part 3 Leg agility – Right (MDS\_308\_R; Numeric: 0, 1, 2, 3, 4; Levels: Normal or Slight or Mild or Moderate or Severe)
- UPDRS part 3 Arising from chair (MDS\_309; Numeric: 0, 1, 2, 3, 4; Levels: Normal or Slight or Mild or Moderate or Severe)
- UPDRS part 3 Gait (MDS\_310; Numeric: 0, 1, 2, 3, 4; Levels: Normal or Slight or Mild or Moderate or Severe)

- UPDRS part 3 Freezing of gait (MDS\_311; Numeric: 0, 1, 2, 3, 4; Levels: Normal or Slight or Mild or Moderate or Severe)
- UPDRS part 3 Postural stability (MDS\_312; Numeric: 0, 1, 2, 3, 4; Levels: Normal or Slight or Mild or Moderate or Severe)
- UPDRS part 3 Posture (MDS\_313; Numeric: 0, 1, 2, 3, 4; Levels: Normal or Slight or Mild or Moderate or Severe)
- UPDRS part 3 Global spontaneity of movement (MDS\_314; Numeric: 0, 1, 2, 3, 4; Levels: Normal or Slight or Mild or Moderate or Severe)
- UPDRS part 3 Postural tremor of the hands – Left (MDS\_315\_L; Numeric: 0, 1, 2, 3, 4; Levels: Normal or Slight or Mild or Moderate or Severe)
- UPDRS part 3 Postural tremor of the hands – Right (MDS\_315\_R; Numeric: 0, 1, 2, 3, 4; Levels: Normal or Slight or Mild or Moderate or Severe)
- UPDRS part 3 Kinetic tremor of the hand – Left (MDS\_316\_L; Numeric: 0, 1, 2, 3, 4; Levels: Normal or Slight or Mild or Moderate or Severe)
- UPDRS part 3 Kinetic tremor of the hand – Right (MDS\_316\_R; Numeric: 0, 1, 2, 3, 4; Levels: Normal or Slight or Mild or Moderate or Severe)
- UPDRS part 3 Rest tremor amplitude LLE (MDS\_317\_LLE; Numeric: 0, 1, 2, 3, 4; Levels: Normal or Slight or Mild or Moderate or Severe)
- UPDRS part 3 Rest tremor amplitude LUE (MDS\_317\_LUE; Numeric: 0, 1, 2, 3, 4; Levels: Normal or Slight or Mild or Moderate or Severe)
- UPDRS part 3 Rest tremor amplitude LipJaw (MDS\_317\_LipJ; Numeric: 0, 1, 2, 3, 4; Levels: Normal or Slight or Mild or Moderate or Severe)
- UPDRS part 3 Rest tremor amplitude RLE (MDS\_317\_RLE; Numeric: 0, 1, 2, 3, 4; Levels: Normal or Slight or Mild or Moderate or Severe)
- UPDRS part 3 Rest tremor amplitude RUE (MDS\_317\_RUE; Numeric: 0, 1, 2, 3, 4; Levels: Normal or Slight or Mild or Moderate or Severe)
- UPDRS part 3 Constancy of rest tremor (MDS\_318; Numeric: 0, 1, 2, 3, 4; Levels: Normal or Slight or Mild or Moderate or Severe)
- UPDRS part 3 Dyskinesia impact on part III ratings A (MDS\_3DyskinA; Numeric: 0, 1; Levels: No or Yes)
- UPDRS part 3 Dyskinesia impact on part III ratings B (MDS\_3DyskinB; Numeric: 0, 1, 2; Levels: No or Yes or NA(A=no))
- UPDRS part 3 Hoehn and Yahr stage (MDS\_3DyskinB; Numeric: 0, 1, 2, 3, 4, 5; Levels: Asymptomatic or Unilateral involvement only or Bilateral involvement without balance impairment or Mild to moderate involvement or Severe disability or Wheelchair bound or bedridden)

#### MONTRÉAL COGNITIVE ASSESSMENT (MOCA)

MOCA score, and the change from baseline to end of treatment, and follow up visits will be summarized by treatments

### 3 DATA HANDLING

#### 3.1 Derived variables

##### 3.1.1 Body Mass Index

Body mass index will be derived at individual level using following derivation rule unless it is conducted automatically in the [REDACTED] database:

$$\text{Body Mass Index} = \frac{\text{Participant's weight in kg}}{(\text{Participant's height in meter})^2}$$

##### 3.1.2 12-lead ECG replicates

Triplicate measurements are taken for each 12-lead ECG variable (e.g. HR, PR interval, QRS, QT and QTcF) with one-minute time interval. Those triplicate readings will be handled by calculating the average of the three measurements as follows:

$$\text{Average ECG} = \frac{(\text{1st reading of ECG parameter} + \text{2nd reading of ECG parameter} + \text{3rd reading of ECG parameter})}{3}$$

##### 3.1.3 MDS-UPDRS part II and III total score (part B only)

MDS-UPDRS part II and part III total scores will be calculated by summing up the numerical results of the MDS-UPDRS part II and III questionnaire items. For part II, this is the sum of 18 ratings performed by the physician and for part III this is the sum of 13 questions.

##### 3.1.4 Antibody Parameters

Values of the maximal concentration ( $C_{\max}$ ) and the time to reach  $C_{\max}$  ( $t_{\max}$ ) are obtained directly from the individual anti-aSyn, anti-UBITH and anti-CpG1 antibody titer-time profiles. If the same maximum titer levels are observed at two or more time points, the earliest time point should be used as  $t_{\max}$ .

For each individual antibody titer-time profiles the area under the curve from 0 to the last quantifiable observation ( $AUC_{0\text{-last}}$ ) and the half-life will be calculated. The  $AUC_{0\text{-last}}$  will be calculated using the linear trapezoidal rule. The half-life will be calculated as  $t_{1/2}=\ln(2)/\lambda_z$ , where  $\lambda_z$  is the terminal elimination rate constant determined by unweighted least squares regression of the terminal part of each individual log/linear concentration-time profile. The following rules will be applied to determine the terminal elimination phase:

- The slope of the regression line must be negative ( $\lambda_z > 0$ ).
- Sample at  $t_{\max}$  cannot be included.
- At least 3 data points should be used.
- $R^2 > 0.85$

In general, the more data points that are used in the estimation, the better. The number of data points will be selected automatically to achieve the largest adjusted  $R^2$  value. If two adjusted  $R^2$  values (based on different number of data points) deviated with less than 0.0001, then the fit based on the most data points will be selected.

### 3.2 Handling of missing data

All missing or incomplete safety and efficacy data, including dates and times, are treated as such. Missing test results or assessments will not be imputed. Missing safety and efficacy data, indicated as 'M' in the data listing, will be assumed to be missing-at-random (MAR) when the statistical mixed model using SAS PROC MIXED is employed.

For graphical and summary purposes efficacy and safety values below the limit of quantification (LOQ; if applicable) will be set to half ( $\frac{1}{2}$ ) of the LOQ. For analysis no undetermined values will be replaced, except pre-values below the LOD/LOQ that are used as covariate. They will be replaced by 50% of the LOD/LOQ.

For calculation of  $AUC_{last}$ , all titer levels below the LOQ will be set to half ( $\frac{1}{2}$ ) of the LOQ. For calculation of half-life all levels below the LOQ will be treated as "missing".

If data points for antibody titers are missing, the AUC parameters will be derived by interpolating with regard to the two neighbouring non-missing values.

If the actual sampling time is missing, but a valid antibody value is measured, the scheduled protocol time will be used for the calculation of the antibody parameters.

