### 3.6 Reporting conventions

P-values  $\geq 0.0001$  will be reported to 4 decimal places; P-values less than 0.0001 will be reported as "<0.0001". Upper case is used for P-value. The mean, standard deviation (SD), and any other statistics other than quantiles, will be reported to one decimal place greater than the original data. Quantiles, such as median, or minimum (Min) and maximum (Max) will use the same number of decimal places as the original data. Estimated parameters, not on the same scale as raw observations (e.g. regression coefficients) will be reported to 3 significant figures. Confidence limits (abbreviated CLs) will be separated by a hyphen, e.g., xxx - xxx).

Tables and listings are programmed following the following rules:

Final deliverable	Word 2010 document (docx)			
Page Option	Landscape		Portrait	
Courier New Font	Number of cols	Number of lines	Number of cols	Number of lines
8	150	45	100	70

Graphic outputs will be produced in png or emf format.

Subjects randomized to Placebo group at each cohort will be pooled and represented only one study group in any reporting outputs.

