#### 4.5 Analysis of efficacy endpoints

All observed and change from baseline efficacy endpoints will be listed by treatment group, subject and visit. Individual graphs by visit will also be generated.

All observed and change from baseline efficacy endpoints with multiple post-baseline measurements (including but not limited to levels of anti-aSyn, anti-UBITH and anti-CpG1 antibody titers in serum and their antibody parameters of  $C_{max}$ ,  $t_{max}$ ,  $AUC_{last}$  and  $t_{1/2}$ , which are derived by non-compartmental analysis and total and free aSyn concentrations in blood) will be summarized using descriptive statistics of n, mean, SD, SEM, median, Min and Max by treatment group, visit (and time when applicable), and will also be presented graphically as mean over time, with standard deviation as error bars.

All observed and change from baseline efficacy endpoints with single post-baseline measurement (including but not limited to levels of anti-aSyn, anti-UBITH and anti-CpG1 antibody titers in CSF and their antibody parameters of  $C_{max}$ ,  $t_{max}$ ,  $AUC_{last}$  and  $t_{1/2}$ , which are derived by non-compartmental analysis and total and free aSyn concentrations in CSF, T-cell ELISpot specific for the immunizing peptide as well as MDS-UPDRS Parts II and III sub scores and total scores) will be summarized using descriptive statistics of n, mean, SD, SEM, median, Min and Max by treatment group, and will also be presented graphically as mean in a bar graph, with standard deviation as error bars.

To establish whether significant treatment effects can be detected on the observed efficacy endpoints with multiple post-baseline measurements, such as serum levels of anti-aSyn, anti-UBITH and anti-CpG1 antibody titers in blood, each parameter will be analysed with a mixed model analysis of covariance (ANCOVA) with treatment, time and treatment by time as fixed factors and subject as random factor and the (average) baseline measurement as covariate.

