The efficacy endpoints of levels of anti-aSyn, anti-UBITH and anti-CpG1 antibody titers in serum and in CSF will initially be analysed without transformation, but if the data suggest otherwise, log-transformation may be applied. Log-transformed parameters will be back-transformed after analysis where the results may be interpreted as percentage change. Residual Q-Q plots are produced to check the assumption of normality of the error term in the mixed effects models as described above. This is done by visual inspection and the Shapiro-Wilk test statistic.

The observed efficacy endpoints with single post-baseline measurement, such as levels of anti-aSyn, anti-UBITH and anti-CpG1 antibody titers in CSF, will be analysed with a mixed model analysis of variance (ANOVA) with treatment as fixed factors and subject as random factor and the (average) baseline measurement as covariate.

The Kenward-Roger approximation will be used to estimate denominator degrees of freedom and model parameters will be estimated using the restricted maximum likelihood method.

The general treatment effect and specific contrasts will be reported with the estimated difference and the 95% confidence interval, the least square mean estimates and the p-value. Graphs of the Least Squares Means (LSM) estimates over time by treatment group will be presented with 95% confidence intervals as error bars, as well as change from baseline LSM estimates.

The following contrasts will be calculated within the model using observed data:

- Treatment with 3 vaccinations of 40 $\mu$ g UB-312 versus pooled Placebo
- Treatment with 3 vaccinations of 100  $\mu$ g UB-312 versus pooled Placebo
- Treatment with 1 vaccination of 40  $\mu$ g, followed by 2 vaccinations of 300  $\mu$ g UB-312 versus pooled Placebo
- Treatment with 3 vaccinations of 300  $\mu$ g UB-312 versus pooled Placebo
- Treatment with 1 vaccination of 40  $\mu$ g, followed by 2 vaccinations of 1000  $\mu$ g UB-312 versus pooled Placebo
- Treatment with 3 vaccinations of 1000  $\mu$ g UB-312 versus pooled Placebo
- Treatment with 3 vaccinations of 2000  $\mu$ g UB-312 versus pooled Placebo

Notes:

- (1) Change from baseline values calculated at subject level for each efficacy endpoint will only be used for descriptive purposes.
- (2) Above contrast will be adjusted to obtain for change from baseline endpoints.
- (3) The treatment groups across the cohorts will also be compared pairwise.

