#### **4.5.1 Inferential methods**

The study is exploratory and no formal null hypothesis is set. No adjustments for multiple comparisons will be applied.

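### Post-baseline titres below LOQ are left unreplaced in the mixed model, so they most naturally drop out and can bias the anti-aSyn contrast with placebo in either direction

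*SAP*

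**What the plan says.** SAP 3.2 has a separate BLQ rule for each use of the data:

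- Graphs and summaries: "For graphical and summary purposes efficacy and safety values below the limit of quantification (LOQ; if applicable) will be set to half" of the LOQ.
- AUClast: "all titer levels below the LOQ will be set to half" of the LOQ.
- Half-life: BLQ levels count as missing.
- Model: "For analysis no undetermined values will be replaced, except pre-values below the LOD/LOQ that are used as covariate". Those baseline values become 50% of the LOD/LOQ.

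The same section says that missing data, coded M in the listings, "will be assumed to be missing-at-random (MAR) when the statistical mixed model using SAS PROC MIXED is employed".

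SAP 4.5 analyses serum titres with a "mixed model analysis of covariance (ANCOVA) with treatment, time and treatment by time as fixed factors and subject as random factor", plus baseline as covariate. Titres "will initially be analysed without transformation, but if the data suggest otherwise, log-transformation may be applied". The seven listed contrasts each compare one Part A regimen with pooled placebo, and SAP 3.6 adds: "Subjects randomized to Placebo group at each cohort will be pooled and represented only one study group in any reporting outputs". The Appendix 2 code is an ordinary Gaussian PROC MIXED with no censoring term. SAP 4.5.1 states: "The study is exploratory and no formal null hypothesis is set".

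**The concern.** The term *undetermined* is not defined. However, the exception to the rule is for baseline values below LOD/LOQ, and it would be unnecessary unless BLQ results were among the undetermined values. A post-baseline result held as below LOQ, and not replaced, gives PROC MIXED no response value. The record is then not used, and nothing elsewhere in the SAP recovers it.

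The loss depends on the value itself. The SAP does not say that BLQ results are coded M, but MAR is the only missing-data assumption it gives for this model. MAR cannot hold for values that are absent because they are low. Records are lost rather than whole participants, unless every post-baseline value of a participant is BLQ. In the single-measurement model that the SAP uses for CSF, one BLQ result is enough.

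Anti-aSyn titre in blood and CSF is a primary outcome. The tables, at half LOQ, and the LS means, intervals and p-values, with BLQ values removed, would describe different data for the same endpoint. Because the model has a treatment-by-time term, a visit with no quantifiable placebo value may have no estimable contrast.

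**Working it through.** **Inputs from the documents.** Placebo participants: Part A 2 + 6 × 1 = 8; Part B 3 + 3 = 6; both parts 14 (SAP 1.10). There is no LOQ, BLQ rate, titre SD or effect size, so there is no plan figure to reproduce.

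**Assumptions.** LOQ = 1; log10 titre normal with SD 0.5 in each group, so s = 0.5 × ln 10 = 1.151 on the natural-log scale. For BLQ rate p, the log mean is μ = −s·z(p), where z(p) is the normal quantile.

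**Formulas for one arm at one visit** (a = −μ/s)

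- Log scale: true μ; BLQ dropped D = μ + s·φ(a)/(1 − Φ(a)); half LOQ = p·ln 0.5 + (1 − p)·D.
- Untransformed: true M = exp(μ + s²/2); BLQ dropped R = M·Φ((μ + s²)/s)/Φ(μ/s); half LOQ = 0.5p + (1 − p)·R.

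**1. Uniform response.** Grid: placebo BLQ 50, 70, 80, 90, 95%; active BLQ 5, 10, 20, 30%.

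Worked corner, log scale, placebo 95% and active 30% BLQ:

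- True: 0.604 − (−1.894) = 2.498.
- BLQ dropped: 1.176 − 0.481 = 0.695, which is 28% of the true value.
- Half LOQ: 0.615 − (−0.634) = 1.249, which is 50%.

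| Share of true difference kept, whole grid | BLQ dropped | Half LOQ |
|---|---|---|
| Untransformed | 89–93% | 91–100% |
| Log scale | 28–58% | 50–93% |

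With equal SDs on the log scale and a uniformly higher active arm, dropping always pulls the log contrast towards zero.

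**2. Half the active arm responds** (responder geometric mean 10 × LOQ, non-responders distributed as placebo), untransformed.

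Worked case, placebo BLQ 90%:

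- Means before dropping: placebo 0.444, responders 19.40. True contrast 0.5 × (19.40 − 0.444) = 9.48.
- Means after dropping: placebo 1.988, responders 19.84. The shares of the active arm still observed are 0.5 × 0.977 = 0.489 (responders) and 0.5 × 0.10 = 0.050 (non-responders).
- Active mean after dropping: (0.489 × 19.84 + 0.050 × 1.988)/0.539 = 18.18. Contrast 18.18 − 1.99 = 16.19, and 16.19/9.48 = 1.71.

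| Placebo BLQ | True contrast | BLQ dropped | Inflation |
|---|---|---|---|
| 50% | 8.73 | 10.88 | 25% |
| 70% | 9.17 | 13.19 | 44% |
| 90% | 9.48 | 16.19 | 71% |

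Half LOQ stays within about 1% in all three rows. For responder means of 5–100 × LOQ, inflation is 19–32% at 50% BLQ and 66–80% at 90%. With 75% responding at 10 × LOQ it is 7% and 21%.

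**3. No placebo value left at a visit.** Probability pⁿ, participants independent.

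| Placebo BLQ | n = 6 | n = 8 | n = 14 |
|---|---|---|---|
| 50% | 1.6% | 0.4% | <0.1% |
| 70% | 12% | 6% | 1% |
| 90% | 53% | 43% | 23% |

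**4. Check in a fitted model.** REML mixed models were fitted to simulated data, with treatment by time over six visits, a baseline covariate and a random subject intercept (simpler than Appendix 2). There were 80 per arm, 4 replicates, and about 87% of placebo values BLQ. The contrast, averaged over visits, was:

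| Response, scale | Complete data | BLQ dropped | Half LOQ |
|---|---|---|---|
| Uniform, log | 1.45 | 0.71 | 1.33 |
| Uniform, untransformed | 2.31 | 1.96 | 2.29 |
| 60% respond, log | 1.33 | 1.08 | 1.30 |
| 60% respond, untransformed | 3.82 | 5.04 | 3.81 |

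At 6 active against 8 placebo (40 replicates per setting, placebo BLQ about 85%), 68–78% of simulated trials had at least one treatment-by-visit cell with no observed value.

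**The case against.** The strongest reply is that the SAP never says BLQ values are dropped from the model. For half-life it says BLQ levels are missing; for the model it does not. Titre results come in separate reports (SAP 1.11.2), and the documents do not show whether an assay returns a flag, a floor value or a number. If it returns a usable number, leaving it unreplaced loses nothing and this bias is zero. This stands as a limit on confidence. It does not rescue the sentence, because that reading would also have to be written down.

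The large figures also need high placebo BLQ rates and many non-responders. Untransformed, with responder means of 5–100 × LOQ, the bias is about −6% to +7% at placebo BLQ of 10–30% with 75% responders. At placebo BLQ of 50–90% it is −4% to +9% with 90% responders and −6% to +4% with 95%. Half LOQ is not always better: at placebo 95% and active 30% BLQ, untransformed, it keeps 91.1% against 92.6% for dropping. The closed-form results are single-visit arm means, not output of the planned model. The n = 6 column concerns Part B, for which SAP 4.5 lists no placebo contrast. All of this stands, and it bounds the size.

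Partial safeguards exist. Half-LOQ summaries are still reported, an empty cell would be visible as non-estimable, and SAP 3.3 requires removed data points to be justified under blind review. That review concerns outliers and unsuitable measurements and sets no BLQ rule. None of these corrects the model estimates.

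**Conclusion.** The concern holds and should be fixed. Followed as written, the rule most naturally removes low titres selectively from the model for a primary outcome. The direction of the bias depends on scale and response pattern: shrinkage with a uniform response, strongest on the log scale, and inflation on the untransformed scale when only part of the active arm responds. The size rests on an assumed log10 SD of 0.5 and assumed BLQ rates. It ranges from negligible to a loss of more than two-thirds of the log difference, or an inflation of up to 80% untransformed, within the scenarios shown. Confidence is medium, because dropping is an inference from an undefined term. With no formal hypothesis, the consequence is for the reported estimates, intervals and p-values.

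**What to change.** In SAP 3.2, replace the sentence on undetermined values with: *For model-based analysis, post-baseline antibody values below LOQ are set to half LOQ, as for summaries, AUClast and the baseline covariate. Results below LOQ are not missing data and are not covered by the MAR assumption.* If readings below LOQ are meant to be used as reported, the SAP should say that instead.

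Report n/N above LOQ by treatment group and visit. Add a sensitivity analysis with a left-censored mixed model on the log scale. Where a group-visit cell is entirely BLQ, give n/N instead of a censored-model estimate.

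The cost is SAP wording, one data step, one table and one extra model, with no new data. There are downsides. Half LOQ is approximate (50–93% of the log difference on the grid above), and a cell filled with one constant strains the equal-variance assumption. The censored model needs a procedure other than PROC MIXED, and it may not converge or give a finite estimate where a cell is all BLQ.
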